4.2. Drug Supplies

N/A

5. STUDY PROCEDURES

5.1. Screening

Participants with HIV will be identified in Kampala Capital City Authority Clinics, Kampala, Uganda (KCCA) clinics and IDI through lab personnel, adherence counselors, and clinicians from those newly enrolled. Potential enrollees will be contacted by clinic staff to assess willingness to participate; if willing, participants will be invited to call study personnel or to come and meet study personnel at clinic.

All of those eligible, based on being ART naïve and in clinic <3 months, will be screened for depression via PHQ-9 and score will be recorded. All of those with depression PHQ-9 score >4 will be referred to Mulago psychiatry clinic for SSRI treatment and monitoring. All screened will be logged in a screening log

5.2. Study Period

Those individuals with mild to moderately-severe depression who consent will be enrolled into the study. They will be asked to provide a plasma sample. We will also administer the Hamilton Depression Scale, a stress assessment using the STRAIN, and a social factors questionnaire. I will also as an extra voluntary measure invite the participants to give a CSF sample via lumbar puncture. This will be requested at baseline and at 26 weeks. Those willing will have an extra consent and receive extra compensation of 100,000 Ugandan shillings. This is in addition to the 10,000- 30,000 Ugandan shillings for transportation every visit.

Follow-up Visit

Week 12 Measurements: At 12 weeks we will again assess the depressed groups for depression using PHQ-9. This is primarily a safety check. We will record the medications the participants are on including antidepressants and ART.

26 Week Measurements: We will again assess for depression using PHQ-9. We will record medications the participants are taking and measure plasma cytokines/biomarkers. We will again administer the social factor questionnaire including a validated social support scale as well as the STRAIN tool. HIV plasma viral load will be checked per National Ugandan HIV guidelines. I will collect these data via review of the electronic medical record.

Those who gave a CSF sample at enrollment will again be invited to give another sample. This will again have an extra consent and receive extra compensation.

Cytokine measurements: We will perform cytokine assays at baseline and 26 weeks using linear regression.

5.3. Subject Withdrawal

Subjects may withdraw from the study at any time at their own request, or they may be withdrawn at any time at the discretion of the investigator or sponsor for safety or behavioral reasons, or the inability of the subject to comply with the protocol required schedule of study visits or procedures.

If a subject does not return for a scheduled visit, every effort should be made to contact the subject. At enrollment they will provide 3 phone numbers. The participants will be called to remind them of their appointments and will be called if they do not return. In any circumstance, every effort should be made to document subject outcome, if possible. The investigator should inquire about the reason for withdrawal and follow-up with the subject regarding any unresolved adverse events (AEs).

If the subject withdraws from the study, and also withdraws consent for disclosure of future information, no further evaluations should be performed, and no additional data should be collected. The sponsor may retain and continue to use any data collected before such withdrawal of consent.

Table 1. Schedule of Study Events

Week	0	12	26
Patient Health Questionnaire-9 (PHQ-9)	X	X	X
Hamilton Depression Rating Scale	X		X
Plasma Inflammatory Biomarkers	X		X
AM Cortisol Levels	X		X
Stress using STRAIN	X		X
Social Factors Questionnaire	X		X
Group Support Psychotherapy		→	
HIV Viral Load (via chart review)			X

6. ASSESSMENTS

6.1. Safety

At screening participants will be screened for depression via PHQ-9. Those enrolled will be asked for a plasma sample and will be evaluated for stress and have a questionnaire to evaluate social factors associated with depression. The participants will be re-

assessed at 12 weeks via PHQ-9 mainly as a safety check. Those with worsening depression or signs of suicidality will be sent to the Mulago psychiatry clinic. At 26 weeks all participants will be screened for depression via PHQ-9, will be asked for a plasma sample, and also have their charts to be checked for viral load information.

We will also have a Data Monitoring and Safety Board. See further description in 8.3 Safety Analysis.

6.2. Pregnancy Testing

This study will ask all women the date of their last menstrual period, their last pregnancy, and do a pregnancy test on all women 18-50 who are otherwise eligible.

6.2.1. Sample Handling

All protocol specimens will be shipped using packaging that meets requirements specified by the International Air Transport Association Dangerous Goods Regulations for UN 3373, Biological Substance, Category B, and Packing Instruction 650. Culture isolates, if obtained in this study, are to be shipped as specified for UN 2814 Category A Infectious Substances.

Biohazard Containment. Transmission of HIV and other blood borne pathogens can occur through contact with contaminated needles, blood, and blood products. Respiratory pathogens such *Mycobacterium tuberculosis* are transmitted by inhalation of droplet nuclei. Appropriate blood, secretion, and respiratory precautions will be employed by all personnel in the collection of clinical samples and the shipping and handling of all clinical samples and isolates for this study, as currently recommended by the Centers for Disease Control and Prevention in the United States, the WHO internationally, and the NIH.

Sample transfer and analysis will be governed by a material transfer agreement, which will be signed between both parties. At the end of the analysis, unused samples will be retained.

7. ADVERSE EVENT REPORTING

7.1. Adverse Events

All observed or volunteered AEs regardless of treatment group or suspected causal relationship will be reported.

For all AEs, the investigator must pursue and obtain information adequate both to determine the outcome of the AE and to assess whether it meets the criteria for classification as an SAE requiring immediate notification. For all AEs, sufficient information should be obtained by the investigator to determine the causality of the AE. The investigator is required to assess causality. Follow-up by the investigator may be required until the event or its sequelae resolve or stabilize at a level acceptable to the investigator.

During each study visit the co-investigator will assess AEs which may have occurred since the previous visit. This will be done by the study coordinator. The patients will be referred and transported if needed to either their HIV primary physician or our psychiatrist at IDI.

7.2. Serious Adverse Events

An SAE is any untoward medical occurrence at any dose that:

Results in death; Is life-threatening (immediate risk of death); Requires inpatient hospitalization or prolongation of existing hospitalization; Results in persistent or significant disability/incapacity (substantial disruption of the ability to conduct normal life functions); Results in congenital anomaly/birth defect,

7.3. Severity Assessment

The severity of adverse events will be graded according to the National Institute of Health Division of AIDS (DAIDS) classification system for reporting adverse experiences in adults.⁴¹

Causality Assessment

N/A

7.4. Reporting Requirements

Each AE is to be assessed to determine if it meets the criteria for SAEs. If an SAE occurs, expedited reporting will follow IRB, local and international regulations, as appropriate. All SAEs will be reported to IDI Scientific Review Committee, the IRB, the Uganda National Council of Science and Technology (UNCST), the Uganda National Drug Authority (NDA). All SAEs will be reported to the sponsor within 24 hours of knowing about the event and to the ethics committee, UNCST and NDA within seven days of knowing about the event. Further relevant follow-up information will be given as soon as possible. Follow-up will continue until the event resolves.

All AEs will be tabulated and reported to the IRB in annual study reports. Serious adverse events will be reported to IRB and the regulatory authorities within seven days from the time the study team becomes aware of the occurrence of the SAE. All AEs will be reported on the AE page(s) of the CRF.]=For example, the same AE term should be used on both forms. AEs should be reported using concise medical terminology on the CRFs as well as on the form for collection of SAE information.

7.5. Post-Recruitment Illness

All subjects with post-recruitment illness will be monitored until symptoms resolve, laboratory changes return to baseline or until there is a satisfactory explanation for the changes observed. Patients will receive medical care including admission at Mulago National Referral and Teaching Hospital or Butabika Psychiatric Hospital and patients will be managed in accordance with Uganda national treatment guidelines.

8. DATA ANALYSIS/STATISTICAL METHODS

8.1. Sample Size Determination

Depression Intervention:

We will power for a reduction in IL-6 between those with persistent and resolved depression at 26 weeks. Based on our systematic review, the reduction in depression score for psychotherapy is 73% from baseline.³² However response rates vary. Another review found the score reduction was 20% when compared to controls.⁴² We then calculated a range of possible sample sizes seen in **Statistics Plan**.

Assuming that 25% of the psychotherapy group will have persistent depression at week 26 (with equal sample sizes, 80% power, and two-sided alpha = 0.05) and I want a delta of .5, we need a total sample size of 168

participants. The prior study had a 22% non-completion rate for group therapy.³⁴ To account for non-completion and up to a 5% loss to follow-up, I estimate a sample size of 200 participants.

Subject Recruitment/Number needed to screen

[figure not shown]
I postulate that the baseline depression rate in these ART naïve subjects would be about 25%.⁴³ Thus we would need to screen 800-1000 HIV+ people.

The non-depressed control group will come out of those screened and not add to the total number screened.

These will be enrolled from the Infectious Disease Institute or three clinics that refer to it. As noted in the preliminary data section, we are currently working on a study in those found clinics and have found we can get about 15 new patients with CD4 <100 cells/uL a month (unpublished data). Our experience is that there are many more presenting with higher CD4 cells/uL counts, or about 150 new individuals a month. Taken these patient sources we estimate we could screen 800-1000 participants over 2.2 years from our 4 clinics and given not all participants will agree to participate we estimate that we can enroll the group over 2.5 years.

8.2. Analysis of Endpoints

- 1) *Effect of Group Support Psychotherapy:* We will compare the proportion of baseline depression with the proportion of persistent depression at week 26. We will use the PHQ-9 as a continuous variable, with changes from baseline to week 26.
- 2) *Effect of biomarkers on persistent vs. resolved depression:* We will compare those with persistent depression (PHQ-9 ≥ 5 at week 26) versus resolved depression (PHQ-9 < 4 at week 26). We will assess baseline demographic and HIV parameters as well as log₂-transformed plasma cytokines from week 0, week 26, and the change in biomarker values from week 0 to week 26. We will use Benjamini-Hochberg adjustment for multiple comparisons for the biomarkers unrelated to our *a priori* hypothesis (i.e. IL-6 association with persisting depression). If the distribution between groups is unbalanced for an important factor (e.g. age, sex as biological variable, anti-depressant use, HIV viral load), we will adjust as needed for differentially distributed variables between the cohorts. We will consider sex as a biological variable in our analyses, considering differential effects in women vs. men.
- 3) *Effect of biomarkers on depressed vs non-depressed control group:* We will compare those never depressed (PHQ-9 < 5) and those depressed at baseline and at 26 weeks. We will also group those never depressed with those with resolved depression (PHQ-9 < 5 at week 26) and compare with those with persistent depression (PHQ-9 > 4 at week 26). We will assess baseline demographic and HIV parameters as well as log₂-transformed plasma cytokines from week 0, week 26, and the change in biomarker values from week 0 to week 26. We will use Benjamini-Hochberg adjustment for multiple comparisons for the biomarkers unrelated to our *a priori* hypothesis (i.e. IL-6 association with persisting depression). If the distribution between groups is unbalanced for an important factor (e.g. age, sex as biological variable, anti-depressant use, HIV viral load), we will adjust as needed for differentially distributed variables between the cohorts. We will consider sex as a biological variable in our analyses, considering differential effects in women vs. men.

*Depression Defined as PHQ-9 score 5-19 (severely depressed excluded)

- 5) *Baseline Cytokine Analysis:* As a secondary outcome, subjects will be categorized into baseline groups of mild depression versus moderate or above depression. We will compare baseline plasma biomarker levels by group via linear regression of \log_2 transformed data. Any demographic covariates associated with depression will be included in the regression model. We will also compare by 9 am cortisol levels. We will assess whether age or sex are associated with biomarker responses.
- 6) *Virologic Outcomes:* As a secondary outcome, proportions of those with 26-week virologic suppression will be correlated by those with persisting depression vs. resolved using Fisher's Exact test.
- 7) *Depression Scale Comparison:* We will compare prevalence of depression using the PHQ-9 and the HDRS. We will compare the proportions of those depressed at baseline and 26 weeks using McNemar's test.
- 8) *Social Factors and Stress Assessment:* We will analyze social factors and the STRAIN stress and adversity tool scores by baseline depression groups as well as those with persistent depression at 26 weeks using linear regression.

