1.2. Background and Rationale

Depression in HIV is common and causes poor HIV outcomes. Depression prevalence in HIV-infected persons ranges from 13 to 78% as compared to 5% in the general population.^{16, 17} Adherence to antiretroviral medication and subsequently viral suppression is a life-saving treatment in HIV.¹⁸ However, depression has been shown to reduce engagement in care as well as adherence to medication.¹⁹ There is also evidence that depression is associated with poorer levels of viral suppression and even mortality.^{20, 21}

Depression in HIV has negative public health implications. Depression decreases the likelihood that people will engage in HIV care, adhere to treatment, and respond to HIV therapy. Those with depression and HIV are less likely to return to health and remain more likely to transmit the virus.^{22, 23} Because of this, treatment of HIV is an important key to prevention; lower rates of engagement in and adherence to HIV treatment due to depression means others remain at risk.^{24, 25}

Growing evidence shows depression has an inflammatory component. Depression has higher prevalence in neuroinflammatory disorders including stroke, diabetes, and HIV.¹⁴ These conditions alter the blood brain barrier allowing for infiltration of immune cells and increased cytokine signaling. While many diseases make people chronically ill such as hepatitis B, only some have increased prevalence of depression such as HIV. This observation does not suggest that the psychosocial impacts of chronic life-threatening illness do not contribute to depression but does imply that neuroinflammatory effects in diseases such as HIV can be additive or synergistic in the pathogenesis of depression.

Depression in HIV, even when participants have virologic suppression, is often resistant to standard psychiatric treatment, and treatment for depression among people living with HIV is understudied. While there are many treatment modalities for depression, a significant proportion of patients do not respond to treatment.²⁶ Also, while there are a few studies looking at treatment of depression specific in HIV, the data are scant.^{27, 28} More work on depression treatment in those with HIV is needed, particularly in low-income countries in sub-Saharan Africa given the high prevalence of HIV.

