Resolution of Depression for Some with ART: Our previous work in Uganda has shown that while a portion of HIV-infected people remain depressed even after starting ART, a large percentage resolve with ART alone. In our previous studies in cryptococcal disease, 65% (N=217) of 325 cryptococcal survivors were depressed via the CES-D scale at time of ART initiation and of those depressed, at 8 weeks 47.5% (N= 103) were no longer depressed, 31% (N=67) remained depressed, and 21.7% (N=47) had died or were lost to follow up (unpublished data). Similarly, 59% in those with cryptococcal antigenemia (N=207) were depressed pre-ART compared to 30% in 125 HIV-infected controls pre-ART with a mean CD4 count of 242 ± 119 cells/ μ L.³⁸ In those with meningitis, we followed depression via CESD and found a significant portion of the depression resolved with HIV therapy but no depression specific therapy. Similarly our co-mentor [name] recently presented a poster at CROI from a subset of participants in the Rakai cohort with available follow up data.³⁹ The researchers found among 333 people with HIV and ART naïve, 22% (N=73) were depressed via CESD score at baseline and 8.4% (N=28) 2 years later. Thus, in this cohort 38% (28/73) had persistent depression at 2 years with HIV therapy alone. [name] co-authored another study looking at ART naïve, HIV-infected Ugandans and found that the rate of persistent depression was 25% over 1 year.⁴⁰

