2. STUDY OBJECTIVES AND ENDPOINTS

2.1. Objectives

- 1) Among depressed HIV-infected Ugandans, determine if the resolution of depression at 26 weeks of HIV therapy is improved with group psychotherapy.
- 2) In the same population determine if persistent depression is associated with higher levels of innate inflammation. Also, compare baseline and follow up inflammation among depressed compared to non-depressed control group.
- 3) Evaluate if viral suppression levels at 26 weeks are improved by group psychotherapy.

Endpoints

- 1) Depression score via patient health questionnaire (PHQ-9) at screening (total screened and total enrolled) and at 26 weeks (total enrolled) comparing those in the observational cohort and those in the intervention cohort.
- 2) Biomarkers associated with depression including IL-6 measured from plasma as well as morning cortisol levels at screening and 26 weeks.

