2.2. Study Hypothesis

Hypothesis: Among HIV-infected Ugandans with depression (A): initiating ART and SSRI therapy, structured weekly group psychotherapy coupled with SSRIs will reduce depressive symptoms, measured by the PHQ-9 and Hamilton Depression Rating Scale: (B) Those with persisting depression at 26 weeks will have increased plasma IL-6 and cortisol levels, reflective of ongoing systemic stress response.

Prediction: Innate inflammation (e.g. IL-6) and systemic stress responses (e.g. cortisol) will be higher at 26 weeks in those with persistent depression compared with those with resolved depression.

STUDY DESIGN

We will enroll a prospective cohort of HIV-infected subjects with depressive symptoms as well as a non-depressed control group.

In the depressed groups we will assess PHQ-9 at baseline (pre-ART), 12 weeks and 26 weeks. (**Figure 1**). PHQ-9 instrument has been used and validated in several African countries including Uganda.¹⁻⁹ The cut-offs for the PHQ-9 tool are “not depressed” (score ≤ 4), “mild depression” (score 5-9), “moderate and moderately severe depression” (score 10-19), or “severe depression” (score ≥ 20). We will also use the Hamilton Rating Depression Scale (HRDS),¹⁰ which has not been previously validated in Uganda. We will compare depression prevalence between the two scales. We will also have a second non-depressed control group who will be followed similarly to the observational group but without SSRIs or the 12 week safety check.

[figure not shown]

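### The PHQ-9 efficacy analysis uses only the change from baseline to week 26; the week-12 score enters no efficacy analysis, and a participant without a week-26 score has no outcome

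*Combined protocol and SAP*

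**What the plan says.** Section 8.2 item 1, repeated in the synopsis, is the only listed analysis of the psychotherapy effect. It has two parts: "We will compare the proportion of baseline depression with the proportion of persistent depression at week 26", and then "We will use the PHQ-9 as a continuous variable, with changes from baseline to week 26". The endpoint list in section 2.1 sets the comparison on the PHQ-9 "at 26 weeks (total enrolled) comparing those in the observational cohort and those in the intervention cohort".

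The study design text after section 2.2 states: "In the depressed groups we will assess PHQ-9 at baseline (pre-ART), 12 weeks and 26 weeks". Table 1 agrees. Section 5.2 gives the purpose of the middle visit: "At 12 weeks we will again assess the depressed groups for depression using PHQ-9. This is primarily a safety check". Section 6.1 links worsening or suicidality at that visit to psychiatric referral, and the monitoring plan in section 8.3 has the DMC review participants with at least 12 weeks of data. No item in section 8.2 uses the week-12 score.

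Section 5.3 describes efforts to reach people who miss visits. No section gives a missing-data rule or an analysis population. Section 8.1 allows for up to 5% loss to follow-up and, separately, cites 22% non-completion of group therapy in a prior study.

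**The concern.** A change to week 26 can be computed only for someone with a week-26 score. A depressed participant who attends week 12 and then leaves therefore has no value in the continuous analysis, although an informative measurement taken months after baseline is on file. The endpoint population in section 2.1 cannot then be delivered as written.

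Two things are at stake. The first is precision: a raw change score wastes information when baseline and week 26 are only moderately correlated. The second is bias: if people doing badly at week 12 leave one cohort more often than the other, the remaining change scores flatter that cohort. The protocol gives a reason to expect that leaving depends on mood, since section 1.2 says "depression has been shown to reduce engagement in care as well as adherence to medication". The study is open label and no rule is written, so how to treat missing scores would be decided with the data in view.

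**Working it through.** **The plan's own figure.** Section 8.1 sizes the study on IL-6 in persistent versus resolved depression, not on PHQ-9 by cohort. With delta 0.5 (read as SD units), 80% power, two-sided 5% and a 1:3 split, the smaller group is (1.960 + 0.842)² × (1 + 1/3) / 0.5² = 41.9, so 42, and 42 × 4 = 168. The figure reproduces. No power is stated for the PHQ-9 comparison, so its precision has to be worked out under assumptions.

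**Inputs.** From the plan: 100 per depressed cohort; 5% loss, leaving 95 per cohort. Assumed: PHQ-9 SD 4.5; correlation of baseline with week 12 of 0.40 and with week 26 of 0.35; correlation r of week 12 with week 26 of 0.4, 0.6 or 0.7; no true effect.

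**Precision at 5% loss.**
- Change score: variance 2 × (1 − 0.35) × 4.5² = 26.3; SE = √(26.3 × 2/95) = 0.74.
- Baseline as covariate: variance (1 − 0.35²) × 4.5² = 17.8; SE = √(17.8 × 2/95) = 0.61.
- Simulation of the same set-up gives about 0.75 and 0.61.
- The variance ratio is (1 + 0.35)/2 = 0.675, a cut of about one-third. At a baseline to week-26 correlation of 0.5 it would be 0.75, and at 0.7 it would be 0.85.
- Week 12 itself adds little here. Before baseline adjustment its variance factor is roughly 1 − r²d, with d the share lost after week 12. For d = 0.05 and r from 0.3 to 0.7 this is 0.996 to 0.976. Most of the gain is baseline adjustment.

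**Bias under unequal selective loss.** Let z be the standardised week-12 score. In the therapy cohort the chance of leaving is expit(−1.55 + z), which averages 21.4%; the other cohort loses 5% at random. The mean z among therapy-cohort stayers is the integral of z(1 − p(z)) over the standard normal, divided by 0.786, which is −0.185. Given z, the expected standardised week-26 score is r × z and the expected baseline is 0.40 × z. The change-score bias is therefore 4.5 × (r − 0.40) × (−0.185):

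| r | Formula | Simulation |
|---|---|---|
| 0.4 | 0 | 0.00 |
| 0.6 | −0.17 | about −0.16 |
| 0.7 | −0.25 | up to −0.27 |

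The change-score SE is √(26.3 × (1/78.6 + 1/95)) = 0.78, so the largest bias is 0.27/0.78, about one-third of an SE. The false-positive rate rises only to about 6%.

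**What week 12 does.** Imputing week 26 by cohort from baseline and week 12, whose point estimate should be close to the mixed model's, brings the simulated bias to within 0.02 points. It does so because leaving was made to depend on the week-12 score. Baseline adjustment in completers alone would not protect: its bias in this scenario is −0.22 to −0.48. Adjustment brings the precision; week 12 brings the protection.

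**Other loss patterns.** With the same selective loss in both cohorts the change-score bias is within about 0.02 points. At 5% in both it is negligible.

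**The case against.** The strongest reply is that the plan expects at most 5% loss, and at that level nothing is materially biased. That is right about bias, but the precision loss remains at 5%.

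Three stronger readings are tempting and not supported.
- A reader might infer that the week-12 score is collected and never used. It serves as a safety check, can prompt referral, and is available to the DMC. What is true is that no efficacy analysis uses it.
- A reader might take the plan to prescribe a completers-only analysis. No section says so; the exclusion follows from the change score and the silence on missing data.
- A reader might treat heavy loss in the therapy cohort as documented. The 22% in section 8.1 is therapy non-completion, and nothing says that someone who stops sessions misses the week-26 PHQ-9. Weekly contact could equally improve retention. The earlier cohort in which "21.7% (N=47) had died or were lost to follow up" consisted of cryptococcal survivors followed to 8 weeks. Such losses fall before week 12, so the week-12 score could not recover them.

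One could also argue that a stated missing-data rule with a week-12 sensitivity analysis would be enough. It would close the gap on missing data, but it would leave the precision of the main comparison unimproved.

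**Conclusion.** The point holds, at modest size. The main PHQ-9 comparison discards a measurement already collected in both depressed cohorts and uses a less precise contrast than the data allow. At the plan's 5% loss the cost is precision: an SE of about 0.75 instead of 0.61 points, mostly from not adjusting for baseline. A false benefit of 0 to 0.27 points arises only if selective loss after week 12 is much heavier in the therapy cohort, which is an upper-range assumption. All sizes rest on the assumed SD, correlations and dropout model; the documents give none of these. A higher baseline correlation shrinks the precision gain. The change is worth making because it is cheap, not because the planned result would be badly wrong.

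**What to change.** In section 8.2 item 1 and the synopsis, replace the change-score comparison with a repeated-measures mixed model of PHQ-9 at weeks 12 and 26 in the 200 depressed participants. Use baseline PHQ-9 as covariate and cohort, visit and cohort-by-visit as fixed effects, and report the cohort difference at week 26. For the persistent/resolved proportion, multiply impute missing week-26 PHQ-9 from baseline and week-12 scores by cohort, then classify. Report deaths separately and do not impute them. Keep the completers analysis as a sensitivity analysis.

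The cost is analysis wording only: no new visit, form or participant is needed. The model assumes that leaving is explained by the observed scores, and it cannot recover outcome information for people lost before week 12. It does nothing about confounding from enrolling the two cohorts one after the other.

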4. TREATMENTS OF SUBJECTS

4.1. Allocation to Treatment/Group

The first half of the depressed participants (100 subjects) will be in the observational cohort.

The second half of the depressed participants (100 subjects) will be in the intervention cohort and receive group psychotherapy.

A second non-depressed control group (100 subjects) will be added for another observational cohort.

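### The psychotherapy effect on PHQ-9 is planned as change from baseline, with no baseline covariate and no stated between-cohort model, although the cohorts are filled in sequence and every depressed participant has a baseline score

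*Combined protocol and SAP*

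**What the plan says.** Objective 1 (section 2.1) asks whether group psychotherapy improves resolution of depression at 26 weeks. Endpoint 1 in the same section is the PHQ-9 score, "comparing those in the observational cohort and those in the intervention cohort".

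The matching analysis is item 1 of section 8.2, repeated in the synopsis under Statistical Analysis. It has two sentences: "We will compare the proportion of baseline depression with the proportion of persistent depression at week 26", and "We will use the PHQ-9 as a continuous variable, with changes from baseline to week 26". Neither names a test, a model or a covariate, and neither mentions the two cohorts.

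Items 2 and 3, on biomarkers, do carry an adjustment rule: if an important factor is unbalanced, "we will adjust as needed for differentially distributed variables between the cohorts". Its examples are "e.g. age, sex as biological variable, anti-depressant use, HIV viral load". Baseline PHQ-9 is not among them, and item 1 has no such rule.

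Allocation is by order of entry (section 4.1): "The first half of the depressed participants (100 subjects) will be in the observational cohort", and "The second half of the depressed participants (100 subjects) will be in the intervention cohort and receive group psychotherapy". The baseline score is available for everyone concerned (Study Design, after section 2.2): "In the depressed groups we will assess PHQ-9 at baseline (pre-ART), 12 weeks and 26 weeks". Entry to both cohorts requires a score of 5 to 19 (section 3.1).

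**The concern.** Taken at face value, a change score fixes the slope of week-26 on baseline PHQ-9 at 1. Over 26 weeks of treatment, in people selected for a raised score, the slope may well be lower. Two things follow. The change score then carries noise that a baseline covariate would remove. And if one cohort happens to start higher, part of its larger fall is regression to the mean and can pass for a treatment effect, or hide one.

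Randomisation does not protect against a gap in starting severity here, because the cohorts are filled in sequence over an estimated 2.5 years (section 8.1).

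The companion comparison of proportions does not help as written. It sets baseline against week 26, and the baseline proportion in the depressed cohorts is 100% by the entry rule. Objective 1 is thus left without a stated between-cohort analysis.

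**Working it through.** **The plan's own figure.** Section 8.1 gives a total of 168 for a delta of 0.5, 25% persistent depression, 80% power and two-sided alpha 0.05. With delta in SD units and a 1:3 split, the smaller group is (1.960 + 0.842)² × (1 + 1/3) / 0.5² = 7.85 × 1.333 / 0.25 = 41.9, so 42, and 42 + 126 = 168. It reproduces. But it concerns IL-6 in persistent versus resolved depression and says nothing about the PHQ-9 contrast between cohorts.

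**Inputs for this point.** From the documents: 100 per cohort (section 4.1), less up to 5% loss (section 8.1), gives 95; 80% power and two-sided alpha 0.05 (section 8.1). Assumed, because the documents give neither: the baseline to week-26 correlation r = 0.3, 0.5 or 0.7, and the SD ratio k = SD(week 26)/SD(baseline) = 1, 1.25 or 1.5. Values of k above 1 are considered because entry restricts the baseline score and nothing restricts the week-26 score.

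**Precision.** In units of the baseline variance:

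- change score: 1 + k² − 2rk
- baseline-adjusted: k²(1 − r²)
- difference between them: (1 − rk)², which is never negative and is zero when rk = 1

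Ratio of adjusted to change variance:

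| r | k = 1 | k = 1.25 | k = 1.5 |
|---|---|---|---|
| 0.3 | 0.65 | 0.78 | 0.87 |
| 0.5 | 0.75 | 0.89 | 0.96 |
| 0.7 | 0.85 | 0.98 | 1.00 |

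Example, r = 0.3 and k = 1.5: 2.25 × 0.91 / (1 + 2.25 − 0.90) = 2.0475 / 2.35 = 0.87.

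With k = 1, the difference detectable with 95 per cohort is 2.80 × √(2/95) = 0.406 SD, times √(2(1 − r)) for change or √(1 − r²) for the adjusted analysis:

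- r = 0.3: 0.48 versus 0.39 SD
- r = 0.5: 0.41 versus 0.35 SD
- r = 0.7: 0.32 versus 0.29 SD

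These figures concern residual variance. The standard error of the adjusted contrast also has a term for the baseline gap itself. For a 1-point gap and an assumed SD of 4 this is about 1/(188 × 16) = 0.0003 beside 2/95 = 0.0211, or 1.6%.

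**Effect of a baseline gap of D points, no true treatment effect.**

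- *Chance or regression to the mean.* Both cohorts follow one regression line with slope rk. The change contrast is then (rk − 1)D. With k = 1 and D = 1 that is −0.7, −0.5 and −0.3 point at r = 0.3, 0.5 and 0.7. The adjusted contrast is centred on zero.
- *Stable cohort difference, parallel change.* The change contrast is centred on zero, and the adjusted contrast is (1 − rk)D: the same size, opposite sign.

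As an illustration, let the gap in cohort means be 1 point, with SD 4 (assumed) and k = 1. In the first case the change analysis rejects in 17.5%, 13.8% and 10.2% of trials at r = 0.3, 0.5 and 0.7, instead of 5%. In the second case the adjusted analysis rejects in 24%, 17% and 11%.

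**The case against.** The strongest reply is that the cohorts are not randomised, so the usual argument for baseline adjustment does not carry over whole. The two estimators rest on different assumptions about why the cohorts differ at entry, and the trial data cannot settle which is right. This stands. A reader might infer that change scores are simply biased here and that adjusting for baseline has no drawback. The documents do not support that. Selection on the same score range from the same clinics makes a chance gap plausible, but sequential filling leaves room for a stable one.

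Second, item 1 is silent rather than wrong. A reader might infer that the sponsor has chosen an unadjusted comparison. The text does not say so: a change score regressed on cohort and baseline PHQ-9 would also fit the wording, and would give the same cohort estimate as the week-26 regression. What is documented is the absence of a model and of a covariate. The remedy is the same on either reading.

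Third, the gain in precision depends on a correlation and SDs that the documents do not give, and it can be close to nil. This also stands.

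Finally, a reader might infer that a comparison of proportions resolved is too weak, so that the continuous analysis must carry Objective 1. One might set the 38% persistence in section 1.2 against the 25% assumed in section 8.1. But the 38% is two-year persistence on the CESD with HIV therapy alone. It is not a control rate for PHQ-9 at 26 weeks with SSRI referral, so no power argument is made from it.

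**Conclusion.** The point holds as a gap in specification with a better analysis available. Item 1 should state a between-cohort model, and that model should include baseline PHQ-9. Its residual variance is at best about two thirds of that of raw change (0.65 at r = 0.3 with equal SDs) and at worst about the same (k = 1.5, r = 0.7), over assumed ranges of r and k.

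The shift of 0.3 to 0.7 point per point of baseline gap assumes equal SDs and a gap that is chance or regression to the mean. In the pure chance case it is conditional on the gap observed; averaged over repeated trials, neither analysis is biased. Under stable cohort differences with parallel change, the adjusted estimate is the one that moves. Neither analysis can therefore be dropped.

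Baseline adjustment does not deal with calendar-time confounding, which comes from allocating the first and second hundred to different cohorts.

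**What to change.** Rewrite item 1 in section 8.2 and in the synopsis so that both say:

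1. *Lead continuous estimate for Objective 1:* linear regression of week-26 PHQ-9 on cohort (intervention versus observational), with baseline PHQ-9, age and sex as covariates, fixed in advance rather than chosen after looking at imbalance.
2. *Resolved, yes or no:* logistic regression on cohort with the same covariates, replacing the baseline-to-week-26 comparison of proportions. The cut-off for resolved must be stated once, because item 2 gives below 4 in section 8.2 and below 5 in the synopsis.
3. *Pre-specified sensitivity analysis:* the between-cohort difference in change from baseline. If the two estimates disagree, the report should say which assumption about the baseline gap each one needs.

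Age and sex are the pre-treatment factors that the plan already names. Its other two examples should stay out of this model: viral load is scheduled only at week 26, and antidepressant use during follow-up comes after entry, so the intervention could affect either.

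The cost is wording in two places, with no new data or visits. The small downside is that the lead estimate relies on baseline differences not being stable cohort differences, which the sensitivity analysis exposes. The text should also acknowledge that calendar-time confounding remains.
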